## **7.3 SAEs or Serious SARs**

### **7.3.1 Timing**

After informed consent but prior to initiation of study medications, only SAEs caused by a protocol-mandated intervention will be collected (e.g. SAEs related to invasive procedures such as biopsies, medication washout, or no treatment run-in).

For any other experience or condition that meets the definition of an SAE or a serious SAR, recording of the event must begin from day 1 of study treatment and continue through the 30 day follow-up period after treatment is discontinued.

For any other experience or condition that meets the definition of a serious adverse event (SAE) or SAR, recording of the event must begin from day 1 of study treatment and continue through the 30 day follow-up period after treatment is discontinued.

### **7.3.2 Documentation and Notification**

These events (SAEs or serious SARs) must be recorded in the eCRF for that patient within 24 hours of learning of its occurrence. For Affiliate sites, an email must also be sent to the NCCN Project Manager indicating that an SAE or Serious

SAR has been entered into Oncore (email contact will be provided at study start-up).

### 7.3.3 Reporting

#### **FDA Expedited Reporting requirements for studies conducted under an IND:**

If an investigator deems that an event is both a serious SAR AND unexpected, it must also (in addition to Oncore) be recorded on the MedWatch Form 3500A as per 21 CFR 312.32. If the event occurs at an Affiliate site, the MedWatch form should be faxed to the UNCCN Project Manager at [contact] along with supporting documentation defining the event and causality. The MedWatch 3500a form can be accessed at:

<http://www.fda.gov/Safety/MedWatch/HowToReport/DownloadForms/default.htm>.

(Please be sure and access form 3500a, and not form 3500). UNC, as the Sponsor of the study, will make the final determination regarding FDA submission.

UNC study personnel are responsible for informing the Principal Investigator of the SAE, and, if it is also a serious SAR AND unexpected, for forwarding all MedWatch 3500A forms to the FDA in accordance with 21 CFR 312.32 (for drugs under an IND) and 21 CFR 314.80 (for marketed drugs).

The UNCCN Project Manager will also be responsible for informing each Affiliate site of all serious and unexpected SARs via fax as soon as possible.

#### **IRB Reporting Requirements:**

##### Affiliate sites:

- For affiliate sites using a local IRB of record, please submit adverse events per local IRB policy.
- For affiliate sites relying on the UNC-IRB, an aggregated list of all SAEs will be submitted to the UNC IRB annually at the time of study renewal according to the UNC IRB policies and procedures. In addition, any SAEs that qualify as an Unanticipated Problem will be entered into Oncore and reported to the UNC IRB by the UNCCN Project Manager using the IRB's web-based reporting system (see section 9.5.3) within 7 days of the Investigator becoming aware of the problem.

##### UNC:

- UNC will submit an aggregated list of all SAEs to the UNC IRB annually at the time of study renewal according to the UNC IRB policies and procedures.
- The UNC-IRB will be notified of all SAEs that qualify as an Unanticipated Problem as per the UNC IRB Policies using the IRB's web-based reporting system (see section 9.5.3) within 7 days of the Investigator becoming aware of the problem.

#### **7.4 Data and Safety Monitoring Plan**

The Principal Investigator will provide continuous monitoring of patient safety in this trial with periodic reporting to the Data Safety Monitoring Committee (DSMC).

Meetings/teleconferences will be held at a frequency dependent on study accrual, and in consultation with the study Biostatistician. These meetings will include the investigators as well as protocol nurses, clinical research associates, regulatory associates, data managers, biostatisticians, and any other relevant personnel the principal investigators may deem appropriate. At these meetings, the research team will discuss all issues relevant to study progress, including enrollment, safety, regulatory, data collection, etc.

The team will produce summaries or minutes of these meetings. These summaries will be available for inspection when requested by any of the regulatory bodies charged with the safety of human subjects and the integrity of data including, but not limited to, the oversight of the Office of Human Research Ethics (OHRE) Biomedical IRB, the Oncology Protocol Review Committee (PRC) or the North Carolina TraCS Institute Data Safety Monitoring Board (DSMB).

The UNC LCCC Data and Safety and Monitoring Committee (DSMC) will review the study on a regular (quarterly to annually) basis, with the frequency of review based on risk and complexity as determined by the UNC Protocol Review Committee. The UNC PI will be responsible for submitting the following information for review: 1) safety and accrual data including the number of patients treated; 2) significant developments reported in the literature that may affect the safety of participants or the ethics of the study; 3) preliminary response data; and 4) summaries of team meetings that have occurred since the last report. Findings of the DSMC review will be disseminated by memo to the UNC PI, PRC, and the UNC IRB and DSMB.

### **8.0 STATISTICAL CONSIDERATIONS**

#### **8.1 Study Design/Study Endpoints**

This is a single arm phase II trial of 40 patients evaluating a novel treatment strategy for EGFR-mutant NSCLC patients who have just progressed on an EGFR-TKI. The primary endpoint of the study will be progression free survival. Secondary endpoints include overall survival, local control rate of sites ablated by SRS, toxicity of SRS, toxicity of erlotinib after SRS, and proteomics based biocorrelates (Veristrat®).

#### **8.2 Sample Size and Accrual**

No data exist at this time to define median progression-free survival on chemotherapy, following first-line erlotinib. However, the FDA has approved docetaxel, pemetrexed and erlotinib for second line therapy based on a median

PFS of 1.8-2.9 months, establishing a standard for minimally effective second line therapy.

Study	Regimen	PFS/TTP
Hanna 	Docetaxel Pemetrexed	2.9 2.9 (PFS)
BR.21 	Erlotinib Placebo	2.2 1.8 (PFS)
Shepherd 	Docetaxel Placebo	10.6w 6.7w (TTP)
TAX 320 	Docetaxel Vin or ifos	8.5w 7.9w (TTP)

While a PFS that matched the best previously demonstrated second line results would be sufficient to meet the threshold for further study, several factors are worthy of note in considering how such results could be interpreted and utilized. First, both SRS and erlotinib are substantially less toxic than cytotoxic chemotherapy. Second, this therapy would represent an additional option for EGFR mutant patients—after second progression on erlotinib, patients would still be eligible for treatment with standard chemotherapy. Thus, we hypothesize that the proposed treatment strategy will lead to a median progression free survival of at least 3 months.

A median PFS of 3 months implies that at 3 months, 50% of the population will still be progression free (PF). With 40 patients, the following table shows the precision of the 95% confidence interval that will be constructed for the percentage of patients who are PF at 3 months. If the percentage of patients PF at 3 months is 65% the 95% CI will be (48%-79%).

Number of Pts Progression Free at 3 months	3 month PFS (95% CI)
16/40	40% (25%, 57%)
18/40	45% (29%, 62%)
20/40	50% (34%, 66%)
22/40	55% (38%, 71%)
24/40	60% (43%, 75%)
26/40	65% (48%, 79%)
28/40	70% (53%, 83%)

We expect the percentage of patients who are PF at 3 months to be more than 50%, so with 40 patients, if 65% or 70% of patients are PF at 3 months, the exact 95% binomial confidence interval will be sufficiently narrow and suggest that the median PFS is longer than 3 months. An exact binomial test with a nominal 0.05 one-sided significance level will have 80% power to detect the difference between the null hypothesis of 50% PF at 3 months and the alternative hypothesis of 70% PF at 3 months when the sample size is 40.

### **8.3 Data Analyses Plans**

Kaplan-Meier curves with appropriate confidence bands will be used to estimate the primary endpoint of median progression free survival. An exact 95% binomial confidence interval for the percentage of patients progression free at 3 months will be also be constructed, and a one-sided test will be done to see if it significantly higher than 50%. While the primary objective is to estimate median PFS, with 40 patients, we may be able to detect a significant improvement over a null hypothesis of only 50% of patients being progression free at 3 months.

Appropriate descriptive statistics including means, standard deviations, medians, and ranges will be provided for continuous data (ex. proteomics), and proportions will be used to summarize categorical data (ex. control and toxicity rates). Standard Kaplan-Meier curves and Cox proportional hazard models will be used to analyze time to event endpoints (including secondary endpoint of OS).

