### **2.2 Secondary Objectives**

**2.2.1** To evaluate local control of sites previously progressive on erlotinib following SRS followed by erlotinib

**2.2.2** To estimate OS after locally ablative therapy and erlotinib in EGFR-mutant NSCLC patients who progressed on prior EGFR-TKI therapy

**2.2.3** To characterize the toxicity of SRS

**2.2.4** To characterize the toxicity of erlotinib when preceded by SRS

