### 2.4.2 Secondary

- OS will be measured from the time of initiation of SRS until death from any cause
- Local control rate of sites ablated by SRS will be measured both overall and by lesion
- Toxicity of SRS will be measured by NCI CTCAE version 4 following completion of SRS, but prior to erlotinib re-initiation.
- Toxicity of erlotinib will be graded using NCI CTCAE version 4.

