### 4.2 Stereotactic Radiosurgery

All sites of progressive disease will be treated with SRS, unless an alternative locally ablative option is chosen. A maximum of five sites will be treated. If less than five sites have progressed on erlotinib, additional sites up to a total of 5 sites may be treated, at the discretion of the treating radiation oncologist. Guidelines for SRS will be defined by body site, consistent with standard of care radiation, as reviewed below.

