## 6.0 EVALUATIONS AND ASSESSMENTS

### 6.1 Time and Events Table

Assessment	Pre-study 	Post SRS 	Q 8 Weeks X 3 	Q 6-12 Weeks 	Early Termination 	At Progression 	Follow-up
Informed Consent	X						
History and PE 	X	X	X	X	X		X
ECOG Performance Status (Appendix A)	X	X	X		X		
Pregnancy Test	X 						
CBC with diff/platelets	X	X	X	X			
Serum chemistries 	X	X	X	X			
Liver function tests 	X	X	X	X			
Tumor evaluation	X 		X 	X 	X 	X 	X 
Concomitant Meds	X		X		X		
Toxicity Assessment	Continuous during the study						
Blood sample for Veristrat® Assay 	X	X 	X 			X 	
Subsequent therapy				X 		X 	X 
Charlson comorbidity index (Appendix B)	X						

See Key to Footnotes on next page.

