 Draw 3.5 mL of blood into SST (gold -top) Vacutainer tube Blood for Verstrat® assay at study entry (prior to SRS or local ablative therapy), post SRS or local ablative therapy (and prior to erlotinib, either that day's dose, or prior to initiating erlotinib), at the first visit following SRS, and at the time of progression (if feasible). See section 6.7 for additional information.

 See sections 6.5 and 6.9.7.

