#### **6.9.7 Responses to subsequent therapies**

It is possible that the study treatment modulates treatment outcomes to subsequent therapies. For example, ablation of clones resistant to erlotinib may also ablate cells that bear resistance to the chemotherapy later chosen. Therefore, to the extent possible, response rate and PFS to subsequent therapy will be recorded on the electronic case report form (eCRF).

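### Section 8.3 reports local control as an undated proportion while scheduled lesion imaging runs only to first progression, so the rate depends partly on PFS; its site set is also wider than objective 2.2.1

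*Combined protocol and SAP*

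**What the plan says.** **Analysis.** Section 8.3 states that "proportions will be used to summarize categorical data (ex. control and toxicity rates". Kaplan-Meier and Cox methods go to time-to-event endpoints, and OS is the only secondary endpoint named there. Sections 2.4.2, 6.9.2, 8.1 and 8.3 give no time point, minimum follow-up or rule for lesions whose observation ends early. Section 6.9.2 does accept that some lesions can be judged only after a period of observation.

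**Imaging schedule.** Scans are every 8 weeks for three visits or until progression (6.3.2), then typically every 6-12 weeks until progression (6.3.3). A new lesion anywhere is progression (6.9.10, 6.9.11).

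**After progression.** In the Time and Events Table the row "Tumor evaluation" is marked in the Follow-up column. Its footnote 12 reads "See sections 6.5 and 6.9.7". Section 6.5 confines post-progression follow-up to response and PFS on later therapy, when possible, and survival. Section 6.9.7 says that "to the extent possible, response rate and PFS to subsequent therapy will be recorded on the electronic case report form (eCRF". Section 6.4 requests images, when possible, to judge the next line of therapy. None of these sections mentions local control of ablated sites.

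**Site set.** Objective 2.2.1 is "To evaluate local control of sites previously progressive on erlotinib following SRS followed by erlotinib". Endpoint 2.4.2 is wider: "Local control rate of sites ablated by SRS will be measured both overall and by lesion". Section 8.1 likewise lists "local control rate of sites ablated by SRS". Where fewer than five sites have progressed, section 4.2 provides that "additional sites up to a total of 5 sites may be treated, at the discretion of the treating radiation oncologist".

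**The concern.** A site that is controlled when disease appears elsewhere leaves scheduled imaging at that point, and a crude proportion counts it as controlled for good. The longer patients stay progression-free, the longer their ablated sites are watched and the more local failures can be seen. The same underlying local control can therefore give different reported rates at different PFS, and a short PFS flatters the result. Whatever later images happen to be obtained and read will also move the figure.

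Without a time point or a statement of follow-up, the rate is hard to interpret or to compare with other crude rates, such as the 94% cited in section 1.4.2.

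A second, separate problem is that an endpoint on all SRS-ablated sites does not isolate the sites that objective 2.2.1 asks about, because discretionary sites enter the denominator.

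**Working it through.** **The plan's own figures.** None is given for local control. The only design calculation, for 3-month PFS, reproduces: with N=40 and success at 26 or more, the exact one-sided alpha is 0.0403 under 50% and the power is 0.807 under 70% (stated: 80%). The exact 95% CI for 26/40 is 48.3% to 79.4% (stated: 48%-79%). Nothing below touches these.

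**Assumptions (not in the documents).** Constant, independent hazards; one ablated site; no local failure recorded after first progression. The last makes the PFS effect an upper bound. Two levels of local failure are used:

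- 19.1% at two years, from section 1.4.1. That figure is locoregional relapse after thoracic radiation in locally advanced disease, so it serves for scale only. hL = -ln(1 - 0.191)/24 = 0.00883 per month, i.e. about 90% control at 12 months.
- 80% control at 12 months, assumed. hL = -ln(0.80)/12 = 0.0186 per month.

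**Crude rate.** The median m can be read in two ways:

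- (a) m is the median time to other progression or death: crude = 1 - hL/(hL + ln2/m).
- (b) m is the median overall PFS: crude = 1 - hL/(ln2/m).

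| Local failure | Reading | m = 3 | m = 6 | m = 12 |
|---|---|---|---|---|
| 19.1% at 2 years | (a) | 96.3% | 92.9% | 86.7% |
| 19.1% at 2 years | (b) | 96.2% | 92.4% | 84.7% |
| 20% at 12 months | (a) | 92.6% | 86.1% | 75.6% |
| 20% at 12 months | (b) | 92.0% | 83.9% | 67.8% |

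The 3- to 6-month shift is 3 to 8 points. At N=40 that is within sampling error: the exact 95% CI for 37/40 is 80% to 98%.

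**If some later images are read.** Let a fraction q of patients have the ablated site read for 6 more months, under (a), with hO = ln2/m:

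crude = 1 - hL/(hL + hO) - [hO/(hL + hO)] × q × (1 - exp(-6hL)).

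With 80% control, q = 0.5 gives 88/82/72% and q = 1 gives 83/77/68% at medians of 3/6/12 months. The 3- to 12-month swing falls only from 17 to 16 or 15 points. At a 3-month median, image availability alone moves the rate between 83% and 93%.

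**What a dated estimate does** (80% control, reading (a)).

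- Kaplan-Meier control at 12 months, censored at other first events, targets 80% at every median under independence.
- With death as a competing event, let a fraction f of other first events be deaths, hD = f × ln2/m. Then 1 - cumulative incidence at 12 months = 1 - [hL/(hL + hD)] × (1 - exp(-12(hL + hD))). For f = 10% this is 82/81/81%, and for f = 30% it is 86/84/82%, at medians of 3/6/12 months. A smaller dependence on PFS remains.
- If local and distant failure are positively correlated (assumed shared gamma frailty, variance 1), Kaplan-Meier censored at first progression reads 91/88/85% at 12 months against a true 80%. At 6 months with a 3-month median it reads about 94% against a true 89%, and the crude rate is also about 94%.
- Patients still progression-free at a 3-month median PFS: 40 × 2^(-6/3) = 10 at 6 months, and 40 × 2^(-12/3) = 2.5 at 12 months.

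**The case against.** Some lesion data will exist after progression. The Follow-up column marks tumor evaluation, section 6.5 collects data every 6 months until death, and judging PFS on the next therapy means looking at existing disease, treated sites included. This stands in part: it makes the no-later-data model a worst case. But collection is only when possible, nothing assigns it to local control, and the partial-capture calculation shows most of the dependence remaining.

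Section 8.3 mentions control rates only as an example, so a time-to-event display is not excluded, and the cited 94% is itself crude. That is fair, but the only method the plan assigns to control rates is the proportion.

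The sizes are assumption-led. No control rate is given for these patients, and a 12-month median is four times the 3-month median in the plan's hypothesis. This stands: the direction follows from the design under these models, while the size does not come from the documents.

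Measuring by lesion would already allow the site split. True, but no text calls for it.

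Post-progression images also reflect the next therapy, whereas objective 2.2.1 concerns control after SRS followed by erlotinib. This stands and shapes the fix.

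**Conclusion.** The concern holds in a limited form. Followed as written, section 8.3 gives a local control rate that depends partly on PFS and on which later images are obtained, with shorter PFS looking better. For one site the illustrated rates at medians of 3, 6 and 12 months are about 96%, 92-93% and 85-87% on the 19.1% scale, and about 92-93%, 84-86% and 68-76% with assumed 80% control at 12 months. Both sets rest on constant independent hazards with no failure recorded after progression. The mismatch with objective 2.2.1 needs no model.

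A reader might infer more than the documents support:

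- **That treated lesions are never seen after progression.** The Follow-up mark and sections 6.4 and 6.5 say otherwise; only the protocol-scheduled imaging before progression is assured.
- **That a 3- to 6-month difference in PFS would visibly distort the result.** The shift is within sampling error at N=40.
- **That discretionary sites bias the rate in a known direction.** The documents do not allow a direction to be stated.
- **That a cumulative-incidence analysis removes the link with PFS.** It reduces it; competing deaths and correlated failure leave some.
- **That the trial's main result is affected.** This is a secondary descriptive endpoint; primary PFS and N=40 stand.

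**What to change.** In section 8.3:

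1. Report lesion-level cumulative incidence of local failure from initiation of SRS, with death as a competing event and censoring at that lesion's last evaluable imaging. Give it at 6 months, and at 12 months only if enough lesions remain at risk, with numbers at risk and patient-clustered intervals.
2. Make the main analysis the one censored at first progression or start of the next therapy. Use post-progression images already obtained only in a supportive analysis, labelled as reflecting later therapy too.
3. For objective 2.2.1, take sites previously progressive on erlotinib as the main set and report added sites separately.
4. State that the estimate assumes progression elsewhere is unrelated to local failure, and that positive correlation would leave it too favourable.
5. If a crude proportion is also shown, give the imaging follow-up per lesion beside it.

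**Cost.** Analysis wording, one lesion-level flag known at treatment planning (previously progressive on erlotinib, yes or no), and a per-lesion read of post-progression images already in hand. No new scans are needed.

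**Downsides.** There are a few more analysis steps, and few lesions remain at risk late if PFS is short. Residual upward bias persists if local and distant failure are positively correlated, in which case the gain over the crude rate is small at a short PFS.

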## **9.0 STUDY MANAGEMENT**

### **9.1 Institutional Review Board (IRB) Approval and Consent**

It is expected that the IRB will have the proper representation and function in accordance with federally mandated regulations. The IRB should approve the consent form and protocol.

In obtaining and documenting informed consent, the investigator should comply with the applicable regulatory requirement(s), and should adhere to Good Clinical Practice (GCP) and to ethical principles that have their origin in the Declaration of Helsinki.

Before recruitment and enrollment onto this study, the patient will be given a full explanation of the study and will be given the opportunity to review the consent form. Each consent form must include all the relevant elements currently required by the FDA Regulations and local or state regulations. Once this essential information has been provided to the patient and the investigator is assured that the patient understands the implications of participating in the study, the patient will be asked to give consent to participate in the study by signing an IRB-approved consent form.

Prior to a patient's participation in the trial, the written informed consent form should be signed and personally dated by the patient and by the person who conducted the informed consent discussion.

## 9.2 Required Documentation

Before the study can be initiated at any site, the following documentation must be provided to the Clinical Protocol Office (CPO) at the University of North Carolina.

- A copy of the official IRB approval letter for the protocol and informed consent
- IRB membership list
- CVs and medical licensure for the principal investigator and any sub-investigators who will be involved in the study.
- Form FDA 1572 appropriately filled out and signed with appropriate documentation (NOTE: this is required if UNC holds the IND. Otherwise, the Investigator's signature documenting understanding of the protocol and providing commitment that this trial will be conducted according to all stipulations of the protocol is sufficient to ensure compliance)
- CAP and CLIA Laboratory certification numbers and institution lab normal values
- Executed clinical research contract

